distributed with mean 0 and variance σ^2_r . The vector of residuals for a given participant are normally distributed with mean **0** and an unstructured covariance matrix **R**. The regimen-specific random effect for a given participant and residuals for that participant are uncorrelated.

The following SAS code specifies the model:

where id is a participant study identifier, trtrnd is the randomly assigned treatment group, visit is the visit identifier, Value is value of the efficacy endpoint being tested for a given participant at a given visit, sx2b1 is years since ALS symptom onset, dFRS is pre-baseline slope, rlz is an indicator of riluzole use at baseline, edv is an indicator of edaravone use at baseline, and NfL is baseline log-transformed serum NfL level. Covariates will be centered at their sample means. The primary estimate will be the treatment-dependent difference in change from baseline to the Week 24 Visit. The estimate and its 95% Wald confidence bounds will be obtained by a linear contrast of adjusted means. The following SAS code specifies the linear contrast for an endpoint measured every 8 weeks and assuming that the sort order for treatment group has the active group last and visits are sorted chronologically:

```
estimate "3|Act vs Plb|dWk 24" trtrnd*visit 1 0 0 -1 -1 0 0 1 / cl;
```

A significant difference in 24-week change from baseline in the direction of greater improvement or less worsening among participants randomized to active treatment would support inference of benefit from active treatment for the efficacy endpoint being tested.

The estimand estimated by the primary linear contrast of the repeated-measures linear mixed model is the mean difference in 24-week change from baseline of a given continuous efficacy endpoint in the active treatment group relative to the placebo group in the FAS. The estimand is defined by the following attributes:

- Treatment: weekly IV infusion of trehalose at a dosage of 0.75 g/kg vs. placebo.
- Population: FAS as defined in Section 6.1.
- Variables: absolute change in endpoint from baseline to the Week 24 Visit.
- Intercurrent event: treatment discontinuation: handled via a treatment policy approach, all data will be used including data collected during the placebo-controlled period after treatment discontinuation. Missing data post-treatment, including data missing due to death, will not be imputed, and will be handled via a missing at random assumption.
- Population-level summary: difference in least-square means of active treatment relative to placebo.

Inference from these analyses is supportive of inference from the Bayesian shared-parameter, repeated-measures model.

6.5.4 Random-slopes Model

The specification of the random-slopes linear mixed model and the primary linear contrast for estimating differences in mean rate of progression in a given continuous efficacy endpoint (ALSFRS-R total and domain scores, SVC, HHD upper extremity, lower extremity, and global average percentages, serum creatinine, serum NfL, ALSAQ-40 total and domain scores, and CNS-BFS total score) are revised from those specified in the M-SAP to include a main effect of treatment and its interactions with study month as additional covariates and to specify that study months are calculated as the difference in days from the Baseline Visit to the date of assessment of a given endpoint multiplied by 12 / 365.25.

The model will include fixed terms for month since the Baseline Visit, treatment group, treatment group × month interaction, centered years since ALS symptom onset and centered years since ALS symptom onset × month interaction, centered delta-FRS and centered delta-FRS × month interaction, centered baseline riluzole use and centered baseline riluzole use × month interaction, centered baseline edaravone use and centered baseline edaravone use × month interaction, and centered baseline log-transformed serum NfL and centered baseline log-transformed serum NfL × month interaction. The following equations describe the model with regimen random effects:

$$Y_{ij} = \gamma_1 + a_{k(i)}^0 + b_i^0 + \gamma_2 t_i + \gamma_3' \mathbf{z}_i$$

$$+ (\gamma_4 + a_{k(i)}^1 + b_i^1 + \gamma_5 t_i + \gamma_6' \mathbf{z}_i) m_{ij} + \epsilon_{ij}$$

$$\{a_k^0, a_k^1\} \sim N(\mathbf{0}, \mathbf{\Sigma}_r), \{b_k^0, b_k^1\} \sim N(\mathbf{0}, \mathbf{\Sigma}_p), \epsilon_{ij} \sim N(\mathbf{0}, \sigma_{\epsilon}^2)$$

$$Cov(\mathbf{a}_k, \mathbf{b}_k) = \mathbf{0}, Cov(\mathbf{a}_k, \epsilon_{i\cdot}) = \mathbf{0}, \text{ and } Cov(\mathbf{b}_k, \epsilon_{i\cdot}) = \mathbf{0}$$
(eqn. 2)

where Y_{ij} is a given efficacy endpoint measured in participant i at visit j, $a^0_{k(i)}$ and $a^I_{k(i)}$ are random intercept and slope for regimen k to which participant i was assigned, b^0_i and b^I_i are random intercept and slope for participant i, z_i is the vector of covariates (centered time since onset, centered delta-FRS, centered baseline riluzole use, centered baseline edaravone use, and centered baseline log-transformed serum NfL) for participant i, m_{ij} is the time from baseline to observation j for participant i in months calculated as days x 12 / 365.25, t_i is an indicator variable for treatment t to which participant i was assigned, γ_I , γ_2 , γ_3 , γ_4 , γ_5 , and γ_6 are estimated parameters and vectors of parameters for the fixed effects, and ϵ_{ij} is the residual for observation j for participant i. The regimen-specific random effects are normally distributed with mean $\mathbf{0}$ and unstructured covariance matrix $\mathbf{\Sigma}_p$. The participant-specific random effects are normally distributed with mean $\mathbf{0}$ and unstructured covariance matrix $\mathbf{\Sigma}_p$. The residuals for a given participant are normally distributed with mean $\mathbf{0}$ and variance σ^2_{ϵ} . The regimen-specific random effects, participant-specific random effects, and residuals are uncorrelated.

The following SAS code specifies the model:

where month is time in months from the Baseline Visit (assuming 12 months in an average of 365.25 days per year) and other fields are the same as identified above in Section 6.5.3. Between-within denominator degrees of freedom will be used for endpoints with only two observations per participant; otherwise, denominator degrees of freedom will be calculated using containment rules. The primary estimand will be the treatment-dependent difference in slopes. The estimate and its 95% Wald confidence bounds will be obtained by a linear contrast of adjusted means. The following SAS code specifies the linear contrast assuming that the sort order for treatment group has the active group last:

```
estimate "3|Act vs Plb|Slope (/mn)" month 0 trtrnd*month -1 1 / cl;
```

A significant difference in slopes in the direction of greater improvement or less worsening among participants randomized to active treatment would support inference of benefit from active treatment for the efficacy endpoint being tested.

The estimand estimated by the primary linear contrast of the random-slopes linear mixed model is the difference in mean rate of progression of a given continuous efficacy endpoint in the active treatment group relative to the placebo group in the FAS. The estimand is defined by the following attributes:

Treatment: weekly IV infusion of trehalose at a dosage of 0.75 g/kg vs. placebo.

Population: FAS as defined in Section 6.1.

Variables: mean rate of change in endpoint from baseline to the Week 24 Visit.

Intercurrent event: treatment discontinuation: handled via a treatment policy approach, all data will be used including data collected during the placebo-controlled period after treatment discontinuation. Missing data post-treatment will not be imputed and will be handled via a missing at random assumption.

Population-level summary: difference in conditional mean slopes of active treatment relative to placebo.

Inference from this analysis is supportive of inference from the Bayesian shared-parameter, repeated-measures model.

6.5.5 Survival and Time to Clinical Events

Survival and time to hospitalizations and clinical events will be analyzed in the FAS, ECC, ERO, STF, and SRO analysis sets. Survival analyses that include follow-up beyond the placebo-controlled period will be analyzed in the ERO analysis set. The summaries and analyses of time to death or death equivalent are the same as specified in the M-SAP with the addition of baseline age, baseline log-transformed serum NfL level, and baseline TRICALS score as covariates in adjusted models, and with the addition that the endpoints of time to death independent of occurrence of death equivalents and time to each of the hospitalization and clinical events will be separately analyzed using the same models. Analysis of time to King's stage 4a or 4b will accommodate interval censoring between ALSFRS-R assessments and will be stratified by baseline King's stage.

6.5.6 HHD0 and HHD0²

Analyses of HHD0 are the same as specified in the M-SAP with the addition of parallel analyses of HHD0², with baseline serum NfL level as an additional covariate, and with the clarification that time to zero strength for both analyses is interval censored between HHD assessments.

6.5.7 Placebo Multiple Imputation

Placebo multiple imputation analyses are the same as specified in the M-SAP with the addition of baseline serum NfL level as a covariate and will be applied to the mixed model repeated-measures analyses of ALSFRS-R total score and SVC in the FAS.

The following SAS code specifies the imputation for an endpoint measured every 8 weeks:

where Wk00, Wk08, Wk16, and Wk24 are the values of a given efficacy endpoint at the Baseline, Week 8, Week 16, and Week 24 Visits, respectively, trtnd has a value of zero (0) for participants randomized to placebo, and x and y take appropriate values to specify the range of a given outcome measure (i.e., 0 and 48 for ALSFRS-R total score; 0 and . [missing value indicator] for SVC).

Inference from these analyses is supportive of inference from the Bayesian shared-parameter, repeated-measures model for the primary endpoint and SVC in the FAS.

6.5.8 Inverse Probability Weights

To reduce bias from possible treatment-dependent loss to follow-up due to death, intolerance, or other causes and possible treatment-dependent initiation of other disease-modifying treatments for ALS, the effect of treatment on ALSFRS-R and SVC will be estimated in the mixed model repeated-measures analysis using visit-specific stable inverse probability weights (Avagyan et al. 2021) in the FAS and ERO analysis sets with censoring of observations collected after any post-baseline initiation of edaravone, riluzole, or sodium phenylbutyrate/taurursodiol. Weights will be calculated as the inverse of the predicted probability of loss to follow-up or initiation of other disease-modifying treatments, winsorized to the 5th and 95th percentiles. Probability of loss to follow-up or initiation other disease-modifying treatments for ALS will be predicted from a conditional random forests model (Hothorn et al. 2006) using all baseline characteristics specified in Section 6.2 Baseline Characteristics.

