This Regimen-specific Statistical Analysis Plan (R-SAP) for the trehalose regimen (RGE) specifies any modification from the default outcome measures, analysis samples, and planned analyses for the placebo-controlled period of the HEALEY ALS Platform Trial as specified in the Master SAP (M-SAP) and adds analyses specific to the open-label extension (OLE) period. The M-SAP and this R-SAP supplement the Master Protocol, the "ALS Master Protocol Recommended Statistical Analysis, Design and Simulation Report" (Appendix 1 to the Master Protocol), and the RGE Regimen-specific Appendix (RSA). Please refer to the Master Protocol and the RGE RSA for details on the rationale for the study design, eligibility criteria, conduct of the trial, clinical assessments and schedule of assessments, definitions and reporting of adverse events, data management conventions, and regulatory oversight and compliance procedures. The "ALS Master Protocol Recommended Statistical Analysis, Design and Simulation Report" (MPRDR) and any regimen-specific deviations described in the RGE RSA and this R-SAP are authoritative in defining the primary and interim analyses. In case of discrepancies between the RGE RSA and this R-SAP concerning use of shared placebos, this R-SAP is authoritative. In case of discrepancies between either SAP and the Master Protocol and the RGE RSA concerning matters of analysis other than the primary and interim analyses and use of shared placebos, the M-SAP and this R-SAP are authoritative. In case of discrepancies between the M-SAP and this R-SAP, this R-SAP is authoritative. On all matters not related to analysis, the Master Protocol and the RGE RSA are authoritative. The following table describes relationships among the relevant documents in adjudicating possible discrepancies with higher numbers indicating greater authority.

	Master	RGE			RGE
Issues potentially requiring adjudication	Protocol	RSA	MPRDR	M-SAP	R-SAP
Use of shared placebos	1	4	2	3	5
Primary and interim analysis specifications not related to use of shared placebo	1	5	4	2	3
Statistical analysis specifications not related to use of shared placebo or primary and interim analyses	1	3	2	4	5
All matters not related to statistical analysis	4	5	1	2	3

2. Study Design

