6.5.9 Principal Stratification

To reduce bias from possible treatment-dependent loss to follow-up due to death, intolerance, or other causes and possible treatment-dependent initiation of other disease-modifying treatments for ALS, the effect of treatment on ALSFRS-R and SVC will be estimated using the potential

outcome framework and principal stratification (Rubin 2006). We will estimate the visit-specific profile of average causal effects in the treatment- and visit-specific principal strata always survivors (i.e., the participants who would have lived to a given visit under both the active and placebo treatment exposures) and never initiators (i.e., the participants who would have not initiated another disease-modifying treatment for ALS prior to a given visit under both the active and placebo treatment exposure) in the FAS and ERO analysis sets. Time to loss to follow-up or initiation other disease-modifying treatments for ALS will be predicted from a conditional survival random forests model (Hothorn et al. 2006) using all baseline characteristics specified in Section 6.2 Baseline Characteristics.

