6.5.10 Additional Sensitivity Analyses of Primary and Key Secondary Outcomes

Sensitivity analyses of primary and key secondary efficacy outcomes are as described in this R-SAP.

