7.2 Secondary, Exploratory, and Safety Analyses

Validation of secondary, exploratory, and safety analyses are the same as specified in the M-SAP with the following clarifications.

Three levels of validation will be used:

- Level 1: Replication of results by an independent programmer.
- Level 2: When a macro is used to generate multiple results, one result will be replicated by an independent programmer.
- Level 3: Log files will be inspected for error messages and / or relevant warnings.

A separate validation document will be created in which the validation level applied for each analysis is specified. The level of validation will be based on whether the result is considered core or supplementary. Core results will be based on validation level 1 or level 2. Supplementary results will be based on level 3 validation. Examples of core results include primary and key secondary efficacy and safety endpoints. Examples of supplementary results include exploratory efficacy endpoints, selected sensitivity analyses, and selected sensitivity analysis data sets for secondary efficacy endpoints. Any analyses that fail due to small sample size or lack of convergence will be omitted with comment rather than programmed separately to find a post-hoc, work-around solution.

8. References

The following references are cited in addition to those specified in the M-SAP:

- Rubin DB. Causal inference through potential outcomes and principal stratification: Application to studies with "censoring" due to death. Statist. Sci. 2006 Aug;21(3):299-309.

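### SAP Section 6.5.8 weights retained observations by the inverse of the probability of being lost; the weight it needs is the inverse of the probability of remaining

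*SAP*

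**What the plan says.** SAP Section 6.5.8 re-estimates the treatment effect on ALSFRS-R and SVC in the FAS and ERO sets, with a "mixed model repeated-measures analysis using visit-specific stable inverse probability weights". Observations after a post-baseline start of edaravone, riluzole or sodium phenylbutyrate/taurursodiol are censored. The declared aim is to reduce bias from treatment-dependent loss and treatment-dependent initiation.

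The weight is defined in one sentence: "Weights will be calculated as the inverse of the predicted probability of loss to follow-up or initiation of other disease-modifying treatments", winsorized at the 5th and 95th percentiles. The next sentence names the same event as the thing predicted: "Probability of loss to follow-up or initiation other disease-modifying treatments for ALS will be predicted from a conditional random forests model", "using all baseline characteristics specified in Section 6.2 Baseline Characteristics". The section gives no formula, stabilising numerator or code, and does not refer to the Master SAP for the weights.

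Two other places bear on which text applies. Section 6.5.10 says: "Sensitivity analyses of primary and key secondary efficacy outcomes are as described in this R-SAP". Section 1 (Governing Documents) says: "In case of discrepancies between the M-SAP and this R-SAP, this R-SAP is authoritative".

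**The concern.** Lost participants contribute no records after loss, and records after initiation are removed. The weights therefore apply only to people who remain. A retained person with a high predicted chance of loss has to count for more, because that person stands in for similar people who have gone. The inverse of the probability of loss does the opposite: those who most resemble the lost participants count least. This works against the section's own aim.

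At stake is a planned robustness check on the MMRM results for key secondary endpoints 2 and 3 (ALSFRS-R change and SVC change, Section 6.5.1). If the sentence is programmed literally, the analysed sample moves further from the lost participants and precision falls. Agreement with the unweighted MMRM would then say nothing about robustness to loss.

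The slip could also go unnoticed. Section 7.2 checks supplementary results by log inspection only, and says: "Examples of supplementary results include exploratory efficacy endpoints, selected sensitivity analyses". Whether 6.5.8 falls in that class is left to a separate validation document. An independent programmer working from this sentence would reproduce the inversion in any case.

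**Working it through.** The plan gives no weight, loss rate or expected result for this analysis, so there is no figure to reproduce. The 120:40 allocation is from the protocol (Number of Planned Participants and Treatment Groups). All loss rates, outcome means, effect sizes and a shared-placebo total of 200 are assumptions. Steps 2 to 5 use a single-visit weighted regression or mean, not the full MMRM.

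**1. Direction.** Let p be the predicted probability of loss or initiation.

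| p | As written, 1/p | Needed, 1/(1−p) |
|---|---|---|
| 0.10 | 10 | 1.11 |
| 0.40 | 2.5 | 1.67 |

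A numerator that is constant within visit, or within visit and arm, leaves the reversed order intact within those groups. Winsorizing is monotone: the rank correlation of the winsorized weight with p is −1.00 for 1/p and +1.00 for 1/(1−p). The literal rule also fails at Baseline, which the Section 6.5.3 contrast includes as a visit. Cumulative loss there is zero, so 1/p is undefined, while 1/(1−p) is 1.

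**2. Who carries the weight.** p was drawn from Beta(1.5, 8.5), Beta(2, 8) and Beta(3, 12), with means 15%, 20% and 20%. Completers are kept with probability 1−p, and weights are winsorized among completers. Effective sample size is (Σw)²/Σw², as a share of completers. Risk quarters are those of all participants.

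| | Unweighted | 1/p | 1/(1−p) |
|---|---|---|---|
| Weight on lowest-risk quarter | 28–29% | 50–63% | 25% |
| Weight on highest-risk quarter | 20–21% | 5–9% | 24% |
| Effective sample size | 100% | 52–76% | 98–99% |

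**3. Precision.** Residual SD 5, risk driver x in the outcome model, logit p = −1.8 + x (18% loss), 4,000 runs. The SE of the adjusted difference goes from 1.01 to 1.28 at 120:40 and from 0.64 to 0.81 at 120:200, a rise of about 27%. With 1/(1−p) it is 1.02 and 0.645.

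**4. Bias when the effect varies with risk.** The outcome is −6 − 2.5x + arm × (1 + h·x), with the same loss model in both arms and a regression on arm and x. The mean benefit is 1 point.

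| h (points per SD of risk) | Unweighted | 1/p | 1/(1−p) |
|---|---|---|---|
| 0.25 | 0.04 | 0.21 | 0.01 |
| 0.5 | 0.08 | 0.42 | 0.02 |
| 1 | 0.16 | 0.84 | 0.03 |

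With h = 0 and x in the model, no weighting produces bias.

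**5. Bias under no true effect, with the driver of loss outside the outcome model.** The outcome is −6 − 2.5x in both arms. The loss model in each arm takes intercepts −2.2, −1.8, −1.4 or −1.0 and slopes −0.5, 0, 0.4, 0.8 or 1.2, which gives 20 × 20 = 400 pairs. Of these, 356 have an unweighted bias of at least 0.05. Ranges cover 120:40 and 120:200.

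| Weight | Median absolute bias | Worse than unweighted (of 356) |
|---|---|---|
| None | 0.33 | n/a |
| 1/p, no arm in model | 0.25–0.26 | 0–1 |
| 1/p, arm in model | 1.15–1.18 | 343 |
| 1/(1−p), no arm | 0.34 | 355–356 |
| 1/(1−p), arm in model | 0.10–0.11 | 0 |

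The residual 0.10–0.11 is due to winsorizing.

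**The case against.** The strongest reply is that the inversion alone does not damage the null comparison. Step 5 bears this out: without arm in the prediction model, 1/p had slightly less bias than no weighting, and correcting only the inversion was slightly worse in nearly every scenario. The bias in step 4 needs an effect that varies with risk, and its largest value assumes variation per SD as large as the whole mean benefit. The planned MMRM already adjusts for time since onset, delta-FRS, riluzole, edaravone and log NfL, each by visit, which leaves less for the weights to correct. All of this stands. It limits the claim about bias and is why the fix has two parts. It does not make 1/p a valid weight for retained records: its smaller null bias is a by-product of concentrating on low-risk participants.

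The reply also runs that this is probably a drafting slip, since the section names an established weighting method and states a bias-reduction aim. That is likely, and no claim is made about the code that will be run. But an explicit rule is given, the following sentence repeats the same event, and nothing in the supplied documents takes the complement.

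Whether arm is left out is open. Section 6.5.9 uses the same phrase about baseline characteristics for strata of people who "would have lived to a given visit under both the active and placebo treatment exposures", so the phrase may not exclude arm. This is a request for clarification, separate from the error.

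Finally, placebo multiple imputation, principal stratification and the ERF set address related concerns, and the analysis sits outside the primary analysis and the hierarchy. That is correct and keeps the importance moderate to low.

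**Conclusion.** The concern holds. The stated rule gives retained participants the reverse of the weight ordering that the section's purpose requires. That conclusion follows from the text and depends on no assumed rate.

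The size does depend on assumptions. With mean loss of 15–20%, half or more of the weight falls on the lowest-risk quarter, and the effective sample size drops to 52–76% of completers. With 18% loss, the SE rises by about 27%. Bias in the treatment difference ranges from nil (driver of loss in the outcome model, homogeneous effect) to 0.21–0.84 points on an assumed mean benefit of 1 point, when the effect varies by 0.25–1 point per SD of risk.

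This should be fixed before the analysis is programmed. The primary Bayesian result and the hierarchical tests are not affected.

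**What to change.** Replace the weight sentence with one to this effect: *each retained observation is weighted by the stable inverse of the predicted probability, at that visit, of still being in follow-up and not having started another disease-modifying treatment; the Baseline weight is 1; weights are winsorized at the 5th and 95th percentiles.* Write out the numerator that makes the weights stable.

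Add a second sentence saying that randomised arm and its interactions enter the prediction model, or that the model is fitted separately by arm.

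Make both changes together. Where the driver of loss lies outside the outcome model, correcting the inversion alone or adding arm alone was worse than no weighting in most scenarios examined, while both together were worse in none.

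The cost is two sentences of SAP text (plus the numerator), with no new data.
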